2.3 PRIMARY AND SECONDARY ENDPOINTS

Primary Endpoint

The primary study endpoint is the alignment accuracy of the knee femoral and tibial components at 6 months for the investigational group compared to the control group.

Secondary Endpoints

- Health Status assessed with the EQ-5D form ⁵
- Operating Room efficiency
 - o OR time
 - o Number of instrument trays used
- Complication rate: incidence of adverse events as well as the proportion of patients who experience at least one complication related to *iASSIST Knee* or conventional instrumentation

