7. STATISTICAL ANALYSIS PLAN

The primary analysis for the study will compare the proportion of alignment accuracy of the knee femoral or tibial components ranging +/- 3 degrees from neutral based on the 6 month postoperative CT scan for *iASSIST Knee* vs. Control (conventional instrumentation).

The primary analysis will test the null hypothesis that the proportion of tibial or femoral component alignment within +/- 3 degrees of neutral for the Investigational group (*iASSIST Knee*) is equal to that of the patients operated without *iASSIST Knee*. The alternative hypothesis is that the proportion of tibial or femoral component alignment within +/- 3 degrees of neutral for the *iASSIST Knee* group is not equal to that of the patients operated without *iASSIST Knee*.

Null Hypothesis: $H_0: \pi_A - \pi_B = 0$

Alternative Hypothesis: $H_A: \pi_A - \pi_B \neq 0$

where π_A represents the proportion of tibial or femoral alignment within +/- 2 degrees from neutral in investigational group on the 6 month postoperative CT scanning and π_B represents the proportion of tibial or femoral alignment within +/- 2 degrees from neutral in control group on the 6 month postoperative CT scanning.

If we reject the null hypothesis, we can conclude that *iASSIST Knee* are more accurate than conventional instrumentation in TKA surgery for either the tibial or femoral component alignment.

Alignment accuracy is defined as the deviation of an angle obtained from the CT scans versus a predefined angle that is accepted for an aligned knee component (refer to the Table 1). Intraoperative validation angles will also be used as targets in the *iASSIST Knee* group. A deviation of +/- 3° is considered to be within the accepted range of an aligned knee component, as reported in the literature^{7, 8}. Massé *et al.* have demonstrated 4.8% *iASSIST* and 30.4% conventional outliers of $\pm 2^\circ$ from neutral for the femur varus-valgus angle, 9.5% *iASSIST* and 60.9% conventional outliers of $\pm 2^\circ$ from neutral for the femur flexion-extension, 4.8% *iASSIST* and 30.4% conventional outliers of $\pm 2^\circ$ from neutral for the tibial varus-valgus angle and 28.6%

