iASSIST and 73.9% conventional outliers of $\pm 2^\circ$ from neutral for the tibia slope⁹. The improvement of the accuracy achieved by the use of the iASSIST Knee validation feature will be evaluated as part of the study for both femur and tibia cuts in both planes. The first tibial proximal and the first femoral distal cuts will be performed and validated. If the validation values are outside of ± 2 degrees from target, the surgeon will adjust the cut as per the iASSIST surgical technique recommendations, re-cut and re-validate.

Table 1. Predefined Target Component Angles

Plane	Component	Persona component Angles
Frontal	Femoral	90
	Tibial	90
Sagittal	Femoral	defined by preoperatively
	Tibial	defined by preoperatively

SAMPLE SIZE

This sample size calculation was conducted anticipating the use of a Fisher’s exact test.

Alpha level: 5% (two-sided)

Power: 80%

Assuming we anticipate that 95% of the investigational group has an angle deviation within $\pm 2^\circ$ and that for the control group, 70% have an angle deviation within $\pm 2^\circ$, the calculation for sample size when comparing proportions is 31 patients. 50 patients per group comfortably exceeds 20% attrition. Therefore, this provides for a total of 100 patients for both arms.

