7.3 DATA ANALYSES

Data will be analyzed using SAS 9.0 or higher. The Type I error rate for the primary study analysis will be 0.05. Comparisons for secondary, exploratory, and safety analyses will be two-sided comparisons using $\alpha = 0.05$, with no adjustment for multiple comparisons.

Primary Analysis: The primary analysis will be presented as both intention-to-treat (ITT) and Full Analysis set (FAS). In the ITT analysis for the primary endpoint, missing data will be treated as described in Section 7.2. A two-tailed Fisher’s Exact Chi-Square test at $\alpha = 0.05$ will be used to assess the study hypotheses and determine whether there is a statistically significant difference between investigational and control groups with regard to the proportion of patients with femoral or tibial component alignment within +/- 3 degrees from predefined angles (Table 1).

Secondary Analysis: Analyses for secondary endpoints will be FAS, and will only use those cases with complete data for the endpoint being analysed.

Continuous data (e.g. age, BMI, VAS pain) will be reported using mean, standard deviation, median, and range. Comparisons of Investigational vs Control with regard to continuous baseline and secondary outcomes will be performed using standard statistical tests and will be chosen as appropriate for the scale and distribution of the measures being analyzed. For example, a t-test, Wilcoxon test, or one-way ANOVA (as appropriate) may be performed to assess differences.

Categorical data (e.g. gender) will be reported using frequency and percentage. Comparisons of Investigational vs Control with regard to categorical baseline, secondary and safety outcomes will be performed using standard statistical tests and will be chosen as appropriate for the scale and distribution of the measures being analyzed. For example, categorical outcomes may be compared for investigational and

control groups using the Fisher's Exact test (for 2x2 tables) or the Likelihood Ratio chi-square test (for tables larger than 2x2).

Knee prosthesis survivorship will be assessed using a Kaplan-Meier analysis. Comparison of survivorship for Investigational vs Control will be done using the Log-Rank test.

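### The primary test is set at ±3 degrees, but the hypothesis parameters and the power calculation are set at ±2 degrees, so the stated 80% power does not apply to the test as written

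*Combined protocol and SAP*

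**What the plan says.** All of this is current text in the combined protocol and SAP.

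**At ±3 degrees**
- Section 7, hypotheses: "The primary analysis will test the null hypothesis that the proportion of tibial or femoral component alignment within +/- 3 degrees of neutral". The opening statement of the primary analysis and the worded alternative use the same window.
- Section 7, definition of accuracy: a deviation of ±3° "is considered to be within the accepted range of an aligned knee component, as reported in the literature".
- Section 7.3, primary Fisher test: "proportion of patients with femoral or tibial component alignment within +/- 3 degrees from predefined angles (Table 1".

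**At ±2 degrees**
- Section 7, parameters in H0 and HA: π_A "represents the proportion of tibial or femoral alignment within +/- 2 degrees from neutral in investigational group", and π_B likewise for control.
- Section 7, Sample Size: "Assuming we anticipate that 95% of the investigational group has an angle deviation within" ±2°, against 70% in control, with a two-sided 5% Fisher test and 80% power. The result is 31 patients, raised to 50 per group to allow for 20% attrition.
- Section 7, outlier rates from a cited poster, given for all four angles.
- Section 7, the intraoperative re-cut limit in the iASSIST arm: "If the validation values are outside of ± 2 degrees from target".

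**Angles.** Section 2.3 names the primary endpoint as "alignment accuracy of the knee femoral and tibial components at 6 months". Sections 7 and 7.3 join the two components with *or*. Table 1 lists a frontal and a sagittal target for each component. Section 7.2 defines exclusion for missing data by tibial alignment alone.

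**The concern.** Whether a knee falls within ±2 degrees and whether it falls within ±3 degrees are different outcomes with different rates in each arm. The formal hypothesis and its verbal statement therefore concern different parameters, and the 80% power was calculated for an outcome that Section 7.3 does not test. Widening the window moves both arms towards 100%. That can shrink the difference and so reduce power, but the plan gives no ±3 rates from which to judge by how much.

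Two windows under one primary hypothesis also leave room to argue after the fact about which result is primary. The unstated angle rule adds to this, because a programmer could not code the primary outcome from the text.

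**Working it through.** **1. The plan's own figure.** Inputs from Section 7, Sample Size: 95% vs 70% within ±2, two-sided α 0.05, power 80%.
- Unpooled normal approximation: n = (1.960 + 0.842)² × [0.95×0.05 + 0.70×0.30] / 0.25² = 7.849 × 0.2575 / 0.0625 = 32.3, so 33 per arm.
- Arcsine approximation: 31.3, so 32 per arm.
- Unpooled with the poster's frontal rates (4.8% and 30.4% outliers, so 95.2% vs 69.6%): 7.849 × 0.2573 / 0.256² = 30.8, so 31 per arm.

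The figure of 31 is therefore a per-arm normal-approximation result. For the Fisher test that the plan names, I enumerated all 2×2 tables and summed the binomial probabilities of those with two-sided p ≤ 0.05. Power is 65.6% at 31 per arm, and 80% is first reached at 39 (80.7%).

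**2. Power at ±2 for the enrolled size.** With 95% vs 70%, exact Fisher power is 82.1% at 40 per arm (50 × 0.8) and 89.9% at 50. The enrolled size supports the ±2 endpoint.

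**3. Carrying the planning rates to ±3.** Assume one angle, with normal deviations centred on target. Then SD = 2 / z((1+p)/2) and P(|X| ≤ 3) = 2Φ(3/SD) − 1.
- iASSIST: SD = 2/1.960 = 1.020, so 2Φ(2.940) − 1 = 99.7%.
- Control: SD = 2/1.036 = 1.930, so 2Φ(1.555) − 1 = 88.0%.

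| Per arm | Power at ±2 | Power at ±3 |
|---|---|---|
| 40 | 82.1% | 31.6% |
| 50 | 89.9% | 51.5% |

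At ±3, 80% power needs 70 evaluable patients per arm.

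**4. How far this depends on the assumption.** Still holding 95% vs 70% at ±2 for one angle:
- Centred t deviations with 2 to 5 df give power of 57–61% at 50 per arm and 39–47% at 40.
- A control mean 1 degree off target gives 47% and 28%; 1.5 degrees off gives 6% and 2%.

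Setting ±3 rates directly, power at 50 per arm (40 per arm) is:
- 99% vs 90%: 27% (15%)
- 98% vs 85%: 51% (36%)
- 99% vs 85%: 64% (45%)
- 98% vs 80%: 78% (64%)
- 99% vs 80%: 87% (74%)
- 99% vs 75%: 97% (90%)

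With iASSIST at 99.7%, 80% power needs a control rate of about 83.5% or lower at 50 per arm, or 80% or lower at 40.

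**5. How far it depends on the angle rule.** The poster's ±2 rates were carried to ±3 as in step 3. Combinations assume independent angles.

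| Rule at ±3 | Rates | Power, 50 per arm | Power, 40 per arm |
|---|---|---|---|
| One frontal angle | 99.7% vs 87.7% | 54% | 34% |
| Femur flexion-extension alone | 98.8% vs 55.7% | >99% | >99% |
| Tibial slope alone | 89.0% vs 38.3% | >99% | >99% |
| Both frontal angles in range | 99.4% vs 76.9% | 96% | 88% |
| All four in range | 87.4% vs 16.4% | about 100% | about 100% |
| At least one frontal angle in range | 100.0% vs 98.5% | about 0% | about 0% |

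The last rule, a literal reading of *or*, has only 29% and 15% even at ±2 (99.8% vs 90.8%).

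**The case against.** The strongest reply is that the text leans towards ±3. It appears in the primary analysis statement, both worded hypotheses, the accepted-range sentence and the test itself, and Section 7.4 sends the analyst to Section 7.3. As part of an endpoint definition, ±2 appears only in the sentence defining π_A and π_B. On this reading there is one test at one threshold, and a favourable choice between windows is speculation. That carries weight: the mismatch between power and test is the better-supported harm. But π_A and π_B are the quantities in H0 and HA, and the sizing agrees with them, so the contradiction remains.

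A second reply is that 51% and 32% are not firm numbers. That is right. They rest on centred normal deviations, which are doubtful for the sagittal angles, where the poster's conventional outlier rates at ±2 are 60.9% and 73.9%. Every distribution tried in step 4 for a single angle stays below 80%, but power could be adequate if the control rate at ±3 were near 75%. Several angle rules also give 88% or more. The wider window does not by itself prove low power.

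Third, the angle rule is arguably a separate issue, and *or* may mean separate femoral and tibial comparisons. It is kept here because no power figure at either threshold can be checked until it is settled. The poster's sample size is not given, so the precision of its rates is unknown.

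**Conclusion.** The concern holds. That the stated 80% power belongs to a different binary endpoint from the one in the primary test needs no assumption; it follows from Sections 7 and 7.3 side by side. The size of the change is conditional. For one angle at the planning rates with centred normal deviations, power at ±3 is about 51% at 50 per arm and 32% at 40, instead of 90% and 82%. Across the other rates and angle rules examined it runs from about 0% to about 100%. The plan itself does not narrow that range. Because this concerns the primary hypothesis, it must be fixed before analysis.

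**What to change.** Choose one threshold and one stated angle, or an explicit combination of angles. Use both in the worded hypotheses, the definitions of π_A and π_B, Section 2.3, Section 7.3 and the sample-size paragraph, and align the missing-data wording in Section 7.2.

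- **Option A: ±2 primary, ±3 as a named secondary analysis.** This keeps the 95% vs 70% assumption, with 90% power at 50 per arm and 82% at 40 for a single angle. Give the reason for choosing ±2, since it is also the re-cut limit in the iASSIST arm. Replace 31 with the Fisher figure of 39 per arm, which 50 less 20% still covers.
- **Option B: ±3 primary, which the plan calls the accepted range.** Redefine π_A and π_B at ±3, state and justify expected ±3 rates for the chosen angle rule, and replace the 80% statement with the power at 50 and 40 per arm under those rates. The 51% and 32% above show what to expect for one angle; they should be replaced by figures from justified rates, not copied into the protocol.

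The wording leans to ±3 and the sizing to ±2, so the sponsor has to say which was meant. The cost is an amendment before analysis. No new data are needed, because the deviations are taken from the 6-month CT scans under either option. The downside is that either the literature-based ±3 range becomes secondary, or the stated power changes and may be less favourable.

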7.4 STUDY REPORT

The primary analysis will be performed after all patients reach the 6 months follow up time point. Data will be analysed using the methods described in Section 7.3.

8. DATA COLLECTION, HANDLING AND RETENTION

8.1 SOURCE DOCUMENTATION REQUIREMENTS

Source documents will be made available to the Sponsor for verification according to local law.

8.2 CASE REPORT FORMS

Data for this clinical study will be collected and documented on CRFs provided in an electronic form or paper form. Authorized study site personnel will complete CRFs only. CRFs must be reviewed by the PI or his/her designees.

8.3 STUDY DOCUMENT RETENTION

Study documents should be retained for 5 years after the study is completed.

9. DATA REPORTING

Within 6 months of the study close the Sponsor will present a final study report to summarize all data collected throughout the study duration, complications throughout the course of the data collection, and general findings.

The report will contain the results of all primary and secondary endpoints. Also, patient follow-up will be analyzed throughout the data collection according to the following definition and equations:

- Lost To Follow-Up:
1. Death
 2. Implant removal: Date of revision, all component part numbers removed, reason for revision, and any relation to study device.
 3. Revision of metal* components (Femur or Tibia): Date of revision, all component part numbers removed, and reason for revision
Consent Rescinded.

**Bearing revisions in which only the polyethylene is replaced will not be withdrawn from the study.*

$$\text{Percentage Follow-up} = \frac{\# \text{ Patients with Follow-Up}}{(\text{Theoretically due} - \text{Lost To Follow-Up})} \times 100$$

$$\text{Percentage Accounted for} = \frac{(\# \text{ with Follow-Up} + \text{Lost To Follow-Up})}{\text{Theoretically due}} \times 100$$

10. RISK ANALYSIS

The site and PI is responsible for following all directions and labeling associated with the product device and its use in TKA. It is expected that all use of the product will be according to the label with full knowledge of all Warnings, Precautions, and Possible AEs associated with the device.

In accordance with the risk management file of the Sponsor the following risk may occur:

- Higher wear rates may be caused by cement or metal particles or other debris that can cause abrasion of articulating surfaces. A high level of wear can shorten the service life of the prosthesis and lead to early revision for the replacement of worn prosthetic components.
- In all cases of joint replacement, asymptomatic localized progressive bone resorption (osteolysis) may be noted around prosthetic components as a result of foreign body reactions triggered by particles. These particles are generated by the interaction between the various components, as well as between the components and bone, mainly through mechanisms of wear, adhesion and fatigue. Other particles may also be produced by the wearing of another body. Osteolysis may lead to successive complications requiring the removal and replacement of prosthetic components.

- Calcification or periarticular ossification, peroneal nerve palsy and hematoma can result from improper handling of implants and associated instrumentation. The risk of embolism, pain and postoperative infections associated with any surgical procedure also applies to the implementation of this prosthesis.
- Although rare, cases of metal intolerance following joint replacement have been observed. Implantation of foreign material in tissues may result in histological reactions involving the formation of macrophages and fibroblasts.
- Dislocation or subluxation of prosthetic components due to improper positioning and/or migration of components can occur. Muscle and fibrous tissue laxity can also contribute to these conditions.
- Prosthetic components can loosen or migrate following trauma.

11. MONITORING PLAN

The Sponsor will monitor the data collection to ensure that the investigation is being conducted consistent with the protocol. The following describes the monitoring activities, which may take place during the course of the study.

11.1 FREQUENCY

Pre-Investigational Visit/Conference:

Prior to initiation of the study, the study manager will provide the PI with all the necessary information to enable him to carry out his responsibilities. This prepares the site with an in-depth training on the protocol, CRFs, and data collection process for the length of the study. The study manager will also train the site on using the Sponsor's electronic CRF upon choice of CRF system.

Monitoring of the Data

Monitoring of the data will occur at least annually.

11.2 SAMPLING PLAN

All data will be monitored for completeness and accuracy on at least an annual basis.

11.3 MONITORING TASKS

The Sponsor will continually monitor the progress of the clinical study. These activities include:

- Tracking of patient enrollment,
- Review of all electronic patient data forms received for completeness,
- Tracking of patient visits to ensure follow-ups are being completed at appropriate intervals,
- Review of all AEs,
- Maintaining open communication with all investigational sites in order to ensure the quality of the clinical study, and
- In-house audits as needed.

Upon completion of any type of monitoring, the site is responsible for resolving all discrepancies found in a timely manner. These will be sent to the site with an audit report by the study manager. All discrepancies found within the online database will be queried and sent directly to the site. Delays in resolving queries are to be avoided at all costs; this provides the study with the most accurate data, prevents delay in reporting procedures & publication.

11.4 STUDY CLOSE-OUT

When a site has completed their data collection, a visit may be necessary by a Sponsor's monitor to ensure all data has been obtained. Data will be reviewed for completeness, and monitored to ensure that all discrepancies have been resolved.

12. LABELING

The devices and products will be used in accordance with their instructions for use and/or approved labeling. The package insert for the device(s) in this study is included in the Investigator Binder.

13. ETHICAL AND REGULATORY REQUIREMENTS

13.1 CODE OF CONDUCT

The PI will ensure that the clinical study is conducted in accordance with

1. Study Protocol and
2. Ethical Guidance for clinical study including human subject (MHLW, Dec. 22, 2014).

13.2 INSTITUTIONAL REVIEW BOARDS/ETHICS COMMITTEE

The PI must obtain appropriate EC approval before the study can be initiated.

13.3 INFORMED CONSENT

Patients (or the patient's legally authorized representative) will be provided with an informed consent and patient information sheet, and given ample opportunity to review the consent and ask questions. The signed informed consent will be obtained before any study procedures begin. If the patient agrees to participate in the study, the patient/representative must sign the informed consent form. The witness and the PI must also sign the informed consent form. A copy of the informed consent form should be given to the patient/representative. All patients who meet all of the entry criteria will be considered for inclusion in this study. Any subject meeting any of the exclusion criteria will be excluded from the study.

The informed consent form must be approved by the site's EC prior to the study initiation.

Patients will be informed of new information learned during the study, which may affect the patient's decision to continue participation in the study.

An Informed Consent Log should be completed to document the existence of the signed informed consent form. The log will contain: Subject ID, date informed consent form signed, and the version signed.

13.4 SUBJECT CONFIDENTIALITY

The CRFs do not include any patient identifying information. Therefore, once the data is entered in the online database a patient can no longer be identified.

By assigning patients a unique ID number, their identity is protected in the online database. The database is restricted, allowing a doctor to only view and enter data from his/her own patients. User authentication is required to view the data. The data is transmitted to a centralized database through a secured (SSL) channel on the Internet. Data in transit is in 128-bit encryption. The access to the centralized database is limited to those who are responsible for maintaining the database.

14. PUBLICATION PLAN

Both the Sponsor and PI will make reasonable efforts to publish the results of this study. Upon completion of all CT measurements and statistical analyses, a manuscript is to be written in English to meet peer-reviewed journal requirements. The manuscript will be submitted to one of below or other suitable journals.

- KSSTA (Knee Surgery, Sports Traumatology, Arthroscopy)
- CORR (Clinical Orthopaedics and Related Research)
- JOA (Journal of Arthroplasty)
- Acta Orthopaedica
- The Knee

